5.0 Investigational Plan

5.1 Overall Study Design, Rationale and Plan: Description

This is a Phase 4, open-label, multi-center, 2-arm study with the primary objective of evaluating the efficacy (SVR12) and safety of the fixed-dose combination tablets of glecaprevir/pibrentasvir (G/P) in HCV-negative subjects who receive a kidney transplant from an HCV RNA-positive deceased kidney donor. Among 90 subjects consented for trial participation, 30 subjects at up to 7 sites are planned to receive an HCV RNA-positive kidney and will be enrolled into a post-transplant treatment arm (Arm 1) receiving open-label G/P for 8 weeks post-transplant. The remaining consented patients who do not receive a study eligible kidney from an HCV RNA-positive donor will be followed in Arm 2 for the minimum duration of 1 year post-enrollment (Arm 2B and 2C), or 24 weeks post-transplant, whichever is longer (Arm 2A). These Arm 2 subjects include patients who do

not receive a kidney transplant (Arm 2C) or who receive a study eligible kidney from an HCV RNA-negative/HCV Ab-positive donor (Arm2A), or from a standard of care donor (Arm 2B). Follow-up for study participants who receive a kidney transplant at a non-study site (Arm 2B5) will be censored at transplantation.

For subjects of Arm 1 of the study, the first dose of G/P will be given as early as 3 days post-transplant. Patients must be out of the ICU, able to eat and drink, take oral medications, and G/P treatment can be safely initiated orally as judged by the site investigator.

Enrolled subjects will be activated in the United Network for Organ Sharing (UNOS) allocation system as eligible for kidney allograft offers from deceased donors that are HCV RNA-positive, HCV Ab-positive, or both.

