5.2.1.3 Exclusion Criteria for kidney transplant candidates

1. History of severe, life-threatening or other significant sensitivity to immunosuppressants utilized in kidney transplant.
2. Female who is pregnant, planning to become pregnant during the study, or breast feeding
3. HIV RNA-positive or HIV antibody positive
4. HCV RNA-positive
5. HBV surface Ag-positive or detectable HBV DNA
6. Primary focal segmental glomerulosclerosis (FSGS) or disease process with increased risk of causing early graft failure as assessed by the transplant nephrologist and/or investigator team.
7. Absence of clinically significant liver disease evident after review of history, labs and fibroscan imaging

- a) Persistently elevated liver enzymes (ALT >2 times upper limit of normal) of unknown cause
- b) Liver fibroscan result >8kPA, or >F2 on liver biopsy
- 8. Transplant candidate requires antibody desensitization protocol for transplantation
- 9. Most recent calculated panel reactive antibody (cPRA) >80%. For this purpose, the cPRA assessed will be the cPRA most-recently reported to UNOS at the time of waitlisting.
- 10. Prior recipient of a non-renal solid organ transplant
- 11. Subject has any other medical condition that, in the opinion of the Investigator, would adversely affect the participant's participation in the study. Specifically, the investigator may exclude any patient with a pre-existing cancer that does not have a high probability of cure or control and increase the risk or decrease the benefit for the transplant as per local transplant center guidance
- 12. Requirement for and inability to safely discontinue the medications or supplements listed in Table 7 of the protocol at least 2 weeks or 10 half-lives (whichever is longer) prior to the first dose of any study drug.
- 13. Participation in another interventional study of any investigational agent or approved medication, or participation in another kind interventional study that the responsible investigator deems to be an exclusion from period 6 months prior to screening to last study visit

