6.1.4 Adverse Event Reporting

For this study, the AE reporting period will be divided based on the three phases of the study.

Pre-Treatment Phase

Screening phase: When all screening tests have been done, we will assess for any AEs related to the screening tests at the time of communication with the subject about whether he/she is official eligible or ineligible for the study.

Pre-existing Condition: A pre-existing condition is one that is present at the start of the study. A pre-existing condition should be recorded as an AE if the frequency, intensity, or the character of the condition worsens during the study period.

Waitlist phase: We will only capture AEs that are pertinent to the study. Specifically, the following will be captured:

1. Patient death,
2. Patient develops a condition that would exclude that subject from the study,
3. Patient is de-listed (taken off the kidney transplant waitlist)
4. Patient is made inactive on the transplant waitlist
5. Serious Adverse events and non-SAE hospitalizations; these will be categorized as “pre-transplant” (vs. “post-transplant”) and “pre-study drug” (vs. “post-study drug”)

In order to ascertain these events, we will review the patient’s medical history by phone every 2 months and in person every 6 months that they are on the wait list.

Treatment Phase in Arm 1

Immediate Post-transplant phase:

From the date of transplant with a HCV RNA-positive kidney to 1 day before first administration of the study drug, we will collect SAEs and clinical outcomes and data, including death, graft failure, acute allograft rejection, delayed graft function, eGFR, ALT elevation > 5 x ULN, SAEs.

HCV Treatment Phase

The following additional data will be collected from Day 1 of HCV treatment to 30 days following last dose of HCV treatment:

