Summary of Statistical Analysis Plan for MYTHIC Study

[Draft: April 26, 2020]

Part	Patient Group(s)	Outcome	Statistical Analysis ^a
1	Arm 1 (ITT)	SVR12	- estimated probability of SVR12 and 95% confidence interval (CI) - exact binomial calculations
2	Arm 1 (ITT)	Virologic failure (VF)	- estimated probability of SVR12 and 95% confidence interval (CI) - exact binomial calculations
3	Arm 1 (ITT)	Post-treatment virologic relapse	- estimated probability of SVR12 and 95% confidence interval (CI) - exact binomial calculations
4	All patients	HCV-viremic kidney transplant (KT); i.e., Arm 1 KT	- cumulative incidence and 95% CI - death and other KT types treated as competing risk - estimate non-parametrically, using Lin (1997) which proceeds through the cause-specific hazards, or Fan (2013) which uses Inverse Probability of Censoring Weighting (IPCW).
5	All patients	Non-HCV-viremic KT; i.e., Arm 2A-2B KT	- same as for component (4).
6	All, by Arm	Hospital admissions	- Arm treated as a time-dependent treatment - crude hospitalization rate per 100 patient-years (PY) and 95% CI - use robust variance estimator, to account for correlation among hospital admissions within-patient
7	All, by Arm	Hospital admissions	- Arm treated as a time-dependent treatment - proportional rates model (Lin et al., 2000) - robust SEs, to account for clustering within-patient
8(a)	All, and SRTR* controls	Kidney transplant	- exclude, from SRTR, all patients who indicated consent to receive an HCV-viremic KT (hereafter: SRTR*) - estimate prognostic score using SRTR* patients: KT as event - 1:5 matching (MYTHIC : SRTR*) based on prognostic score with caliper - Cox regression, with MYTHIC as lone covariate, stratified by matched set

8(b)	All, and SRTR* controls	Kidney transplant	Same as 9(a), but using exact matching on small set of predictors, with prognostic score used to break ties among potential matches
9	Arm 1 – ITT	Compliance	Treated as repeated binary (0/1) data, with 1 indicating compliance (i.e., having taken 80-120% of prescribed pills)
10	Arm 1 – ITT	Death	Time to event; Cox regression
11	Arm 1 – ITT	Graft failure	Time to event; Cox regression
12	Arm 1	Delayed graft function	DGF: binary (0/1) response. Compute OBS/EXP, where OBS=observed number of DGFs for Arm 1 and EXP= expected count based on logistic regression model fitted to HCV-negative UNOS patients from large academic centers

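### SAP Part 8 applies neither the trial's recipient criteria nor a list-status match to its SRTR controls, so the time-to-transplant hazard ratio may partly reflect who can be transplanted

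*SAP*

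**What the plan says.** Part 8(a) of the SAP builds the comparator in four steps:

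- Pool: "exclude, from SRTR, all patients who indicated consent to receive an HCV-viremic KT".
- Score: "estimate prognostic score using SRTR* patients: KT as event".
- Matching: "1:5 matching (MYTHIC : SRTR*) based on prognostic score with caliper".
- Model: "Cox regression, with MYTHIC as lone covariate, stratified by matched set".

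Part 8(b) keeps the same pool and changes only the matching, "using exact matching on small set of predictors, with prognostic score used to break ties among potential matches". The score predictors, the exact-match predictors, the caliper width and the controls' time zero are not given. The outcome is labelled simply as kidney transplant.

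Protocol 8.1.4 names demographics, waiting list priority, blood group, geographic region and sensitization as matching factors. The list is open-ended and does not mention list status. Objective 4 (protocol 4.2) concerns deceased donor transplantation.

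Participants enter under the recipient criteria of protocol 5.2.1. These include age limits, eGFR below 15, listing for a kidney alone, no available living donor, a cPRA limit, no prior non-renal organ transplant, negative viral tests, and the nephrologist's assent. Eligibility is verified centrally (5.1.3, 5.5.4) and rechecked while waiting (5.1.4.1). Section 5.1 states: "Enrolled subjects will be activated in the United Network for Organ Sharing (UNOS) allocation system". The rest of that sentence shows that this means being opened to offers from HCV-positive donors. Section 6.1.4 lists, among the waitlist events to be captured, "Patient is made inactive on the transplant waitlist".

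**The concern.** Objective 4 asks whether enrolment shortens the time to transplant compared with similar waitlisted candidates. The control pool as written contains candidates who could not have entered the trial. Protocol 5.2.1.2 gives one example: listing is allowed below eGFR 20, whereas the trial requires below 15. The pool may also contain candidates who are on the list but inactive, and so not receiving offers at time zero.

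Nothing later in the analysis repairs an imbalance that survives matching. The model has one covariate, so any remaining difference in readiness for transplant, or in routes to transplant, goes into the MYTHIC hazard ratio. The SAP does narrow its reference population elsewhere: Parts 12 and 13 use HCV-negative patients from large academic centers. Part 8 has no such restriction.

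At stake is the interpretation of a secondary comparison. A hazard ratio above 1 could be read as better access through the trial when part of it reflects the composition of the controls. A hazard ratio near 1 could equally hide a real effect.

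**Working it through.** **The plan's own figure.** Protocol 8.2 gives 80% power for 40 of 90 (44.4%) against 20% of 270 comparators (1:3) over about 6 months. For two proportions, two-sided 5%:

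- Pooled proportion: (40 + 54)/360 = 0.261.
- Null SE: √[0.261 × 0.739 × (1/90 + 1/270)] = 0.0535.
- Alternative SE: √[0.444 × 0.556/90 + 0.20 × 0.80/270] = 0.0578.
- z = (0.2444 − 1.96 × 0.0535)/0.0578 = 2.42, so power is about 99%.

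The 80% is not reproduced and can only be a floor. The point here does not depend on it. The planned rates imply a hazard ratio of ln(1 − 0.444)/ln(1 − 0.20) = 2.63, which gives a scale for the bias below.

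**Inputs for the check.**

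- 90 participants (8.2), 1:5 matching (SAP Part 8), so 450 controls; two-sided 5% test (8.1).
- Follow-up of 1 year. One-year transplant probability p among active candidates of 20% to 36%. The upper value extends the protocol's 20% at 6 months at a constant hazard: 1 − 0.80² = 0.36.
- Share q of matched controls who are inactive. **This is an assumption; neither document gives a figure.**
- No trial effect: participants and active controls have the same hazard.

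**Expected distortion.** If inactive controls stay inactive all year, the control probability is p(1 − q), and the apparent hazard ratio is roughly ln(1 − p)/ln[1 − p(1 − q)]. At q = 20%:

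- p = 0.20: ln(0.80)/ln(0.84) = 0.2231/0.1744 = 1.28.
- p = 0.36: ln(0.64)/ln(0.712) = 0.4463/0.3397 = 1.31.

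**Rejection rate of the Cox test stratified by matched set** (simulated, no trial effect, range over p):

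| Inactive share of matched controls (assumed) | Rejects | Apparent HR |
|---|---|---|
| 0% | about 5% | 1.0 |
| 10% | 7-11% | about 1.1 |
| 20% | 17-27% | about 1.3 |
| 30% | 32-53% | 1.45-1.51 |
| 40% | 53-77% | 1.73-1.80 |

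Over 6 months instead, with 20% to 44% of active candidates transplanted, a 20% share gives 18-36%. Rejections at a 20% share are almost all in favour of MYTHIC.

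**Softening the worst case, at a 20% control share.**

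- Inactive controls reactivate with a median of 1 year, and participants and active controls become inactive at 0.1 per year (assumed): rejection 12-18%, HR 1.17-1.21.
- 10% of participants also inactive throughout (assumed): 8-12%. With 20% of participants inactive the groups are alike, and rejection returns to 4-5%.

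**Forces in the other direction.** Participants must have no available living donor (5.2.1.1), while Part 8 does not limit the event to deceased donor transplants. Adding an assumed 5-10% one-year living donor rate among active controls to the 20% inactive share brings rejection to about 6-14%, with a hazard ratio of about 0.9 to 1.2. Section 5.2.1.4 also says that candidates with high PRA often have enhanced access to deceased donor organs, so controls above the trial's cPRA limit may be transplanted sooner. That effect was not quantified.

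**The case against.** The strongest reply is that the pool is only the starting point. A prognostic score with transplant as the event, matched within a caliper, could remove most of the problem. If list status is a predictor, candidates who cannot receive an offer would score very low and should largely fall outside the caliper. The protocol's list of matching factors is not closed, and the SAP is headed as a draft summary, so silence in a table cell is not a decision to ignore status. This stands as a limit: the table above describes matched controls, and so assumes that matching has not dealt with list status. It does not remove the point, because a predictor that is not named is not a pre-specified safeguard, and the absence of recipient criteria from the pool is plain on the page.

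Two stronger readings are tempting, and the documents support neither. First, a reader might infer from section 5.1 that active list status is a condition of entry. The sentence concerns the type of offer, and neither 5.2.1.1 nor 5.2.1.3 requires active status. That participants usually start active is a reasonable inference, since becoming inactive is a recorded event, but it is not stated. Second, a reader might conclude that the comparison is biased towards MYTHIC. That follows for inactive controls taken alone. The living donor and cPRA rules act the other way.

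**Conclusion.** The point holds as a flaw in how the control group is built, with unknown net direction. Following Part 8 as written admits controls who could not have joined the trial and does not align list status at time zero, and the model cannot correct what matching leaves behind. The one-year size for inactive controls alone is about 17-27% false rejection at an assumed 20% share, with an apparent hazard ratio near 1.3. It falls to the nominal 5% if the share is zero or if participants are inactive equally often. A hazard ratio near 1.3 is well short of the planned 2.63, so a 20% share would not by itself produce the effect the protocol expects, but it could make a null or modest effect look significant. The result rests on the assumed share, on constant hazards, and on the unlisted predictors not covering list status. Because the comparison is secondary and non-randomised, this should be corrected, but it does not touch the primary SVR12 analysis.

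**What to change.** Amend SAP Part 8, before the score is fitted and matching is done:

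1. Define an index date for participants and controls.
2. Restrict the SRTR pool to candidates who on that date meet the protocol 5.2.1 recipient criteria that the registry records: for example age, listing for a kidney alone, the cPRA limit, no prior non-renal organ transplant, and others where available. The synopsis and 5.2.1 differ on whether the age and cPRA boundary values are included, and these passages must be reconciled before the filter is coded.
3. In both 8(a) and 8(b), match exactly on active or inactive list status at the index date. This is a matching factor, not a trial eligibility criterion, so it also handles any participant who is inactive.
4. Fit the prognostic score in the same restricted pool, and list its predictors, the exact-match predictors and the caliper.
5. Use deceased donor kidney transplant as the event, as objective 4 states, and say how living donor transplants are handled in both groups.

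The cost is a few lines of SAP text, a filter on registry fields and slightly more data preparation. The control pool becomes smaller. The documents do not say how many candidates would remain or which criteria the registry holds, so the sponsor should confirm that 450 controls for 90 participants are still available. Criteria that the registry does not record, such as the nephrologist's assent, will remain unmatched and should be stated as a limitation.

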8.1 Statistical and Analytical Plans

The data analysis will be generated using SAS version 9.4 or higher for windows and/or STATA software version 14.0 or higher (StataCorp LP, College Station, TX). SAS Institute Inc. SAS and all other SAS Institute Inc. product or service names are registered trademarks or trademarks of SAS Institute Inc., Cary, NC, USA. All statistical tests (if applicable) and confidence intervals will be two-sided with an alpha level of 0.05.

Descriptive statistics will be provided, such as the number of observations (N), mean, and standard deviation (SD) for continuous variables and counts and percentages for discrete variables.

The efficacy and safety of the “reactive” G/P treatment of patients who become HCV RNA-positive after receiving a kidney from a study eligible HCV RNA-negative/HCV Ab-positive donor in Arm 2A are not an objective of this study, and they are not included in assessments of efficacy or safety described below. The time to transplant and clinical outcomes and data post-transplant from patients in Arm 2A are included in those secondary endpoints.

The primary analysis will occur after all recipients of HCV RNA-positive kidneys in Arm 1 have completed post-treatment week 12 visit (corresponding to SVR₁₂ data collection) or prematurely discontinued study. The primary analysis of SVR₁₂ will be performed on the intention-to-treat (ITT) population defined as all enrolled subjects who received a study eligible HCV RNA-positive kidney and received at least one dose of G/P according to actual treatment received (Arm 1).

No data will be imputed for any efficacy or safety analysis except for analyses of SVR endpoints (HCV RNA data). HCV RNA values will be selected for the analyses of all SVR endpoints (e.g., SVR₄ and SVR₁₂, SVR₂₄) based on defined visit windows. A backward imputation method will be used to impute missing responses for SVR analyses. Additional details of analyses to be performed will be specified in the Statistical Analysis Plan.

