8.1.4 Secondary Clinical Outcomes

Secondary clinical outcome analyses will be performed for subjects prior to kidney transplant in both Arms 1 and 2, and post kidney transplant for those who receive a kidney transplant in Arms 1 and 2. For details on safety reporting and periods of safety reporting see section 6.1.4.

The cumulative incidence function curves of time to kidney transplant will be created for each type of kidney transplant (Arms 1, 2A, 2B), and cumulative incidence and standard error (SE) will be calculated for each type of kidney transplant.

An exploratory analysis will create cumulative incidence function curves of time to kidney transplant for the subgroups of Arm 2B if sufficient subjects are enrolled in Arm 2B.

The number and percentage of subjects with clinical outcomes while on waitlist and after study consent (SAEs, delisting from waitlist, death) among subjects who receive an HCV RNA-positive kidney (Arm 1) and among those subjects who do not receive an HCV RNA-positive kidney (all Arm 2 subjects) overall and with breakdown by category of Arm 2 (2A, 2B, 2C). In addition, the total number of inpatient hospital days while on waitlist in those who did receive an HCV RNA-positive kidney (Arm 1) and total inpatient hospital days in those who did not (Arm 2) overall and with breakdown by category of Arm 2 will be summarized descriptively with mean, median, standard deviation (SD), minimum and maximum.

We will match MYTHIC trial participants 1:3 to comparators derived from the Organ Procurement and Transplantation Network database. Matching will be based on demographics and baseline characteristics known to influence waiting time, including waiting list priority, blood group, geographic region, and sensitization. A comparison of time to kidney transplantation between the kidney transplant candidates enrolled in the MYTHIC trial and OPTN comparators will be performed using a Cox proportional hazards model.

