8.2 Determination of Sample Size

This study is primarily designed to demonstrate feasibility and to generate preliminary data related to cure rates (defined as SVR₁₂) from treating donor-derived HCV infection post kidney transplantation using G/P. For this reason, the sample size was not determined with reference to power to detect differences between groups for the primary objective. The lower bound of a one-sided 95% confidence interval using the Wilson's score method, for various SVR₁₂ rates with a total sample size of 30 subjects are provided in Table 10.

Table 10: Estimated Lower Bound for 95% Confidence Interval for Cure Rate Based on Observed Number of Cures

Sample Size	No. of Observed Cures	Observed Cure Rate	Lower Bound for 95% CI of Cure (Wilson's Score)
30	30	100.0%	93.8%
30	29	96.7%	85.4%
30	28	93.3%	81.0%
30	27	90.0%	76.9%
30	26	86.7%	73.0%

As a secondary objective, we will compare time to kidney transplantation between the estimated 75 - 90 kidney transplant candidates enrolled in this trial with 225-270 matched kidney transplant candidates from the OPTN list (1:3 match). We estimate that at least 40

patients (44%) of 90 enrolled patients will undergo kidney transplantation versus 20% (or less) of comparators from OPTN list during an estimated 6 months of follow-up, with 80% power to detect a difference between groups.

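### The protocol and SAP specify different registry comparisons for objective 4, and the SAP gives two matching versions without naming one as primary

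*SAP*

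**What the plan says.** **Protocol.** Section 4.2 (objective 4) and the synopsis define the outcome as time to deceased donor kidney transplantation. Section 8.1.4 states: "We will match MYTHIC trial participants 1:3 to comparators derived from the Organ Procurement and Transplantation Network database". The factors are demographics and characteristics affecting waiting time, with waiting list priority, blood group, region and sensitization named. No matching algorithm is given, and the model is a Cox model with no mention of stratification. Section 8.2 sizes the comparison as the "estimated 75 - 90 kidney transplant candidates" in the trial against "225-270 matched kidney transplant candidates from the OPTN list (1:3 match". Sections 8.1.4 and 8.2 speak of kidney transplantation without the deceased donor restriction.

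**SAP, Part 8(a).** Registry candidates who consented to an HCV-viremic kidney are removed from SRTR. Matching is then "1:5 matching (MYTHIC : SRTR*) based on prognostic score with caliper", with no caliper width. The outcome is kidney transplant, and the Cox model is stratified by matched set.

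**SAP, Part 8(b).** This is described as the same as 9(a), but "using exact matching on small set of predictors", with the score used to break ties. The predictors are not named. There is no Part 9(a), and Part 9 concerns compliance; 8(a) is presumably meant.

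Protocol 8.1 says that the SAP will give further details of analyses. Neither document says which prevails if they conflict, and neither labels any version primary or sensitivity. The SAP is titled a summary and marked as a draft of April 26, 2020.

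**The concern.** This is more than a slip in the ratio. Five elements differ between the documents: control pool, ratio, matching variables, model stratification and endpoint. Two of these change the question being asked.

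- **Control pool.** Removing candidates who agreed to HCV-viremic kidneys sets the trial against people without that route to transplant. The protocol's pool is not restricted in this way.
- **Endpoint.** Section 5.2.1.1 admits only participants with no available compatible living donor, and no such restriction is stated for the registry controls. Counting living donor transplants could therefore add events unevenly between the groups.

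The documents give no figures from which to size either effect.

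This is the one between-group comparison for which the protocol states a power. The study is open-label and the controls are assembled from a registry, so different control sets can be built after outcomes are known. A named primary specification is the protection against that.

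**Working it through.** **Inputs.** Protocol 8.2: 75-90 participants; "patients (44%) of 90 enrolled patients will undergo kidney transplantation", at least 40 patients, so p1 = 40/90 = 0.444; "20% (or less) of comparators from OPTN list", so p2 = 0.20; stated power 80% over about 6 months. Protocol 8.1: "All statistical tests (if applicable) and confidence intervals will be two-sided with an alpha level of 0.05". Ratios: 1:3 (protocol) and 1:5 (SAP). No dropout rate is stated, so none is applied. The formulas below ignore matched-set correlation.

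**1. The plan's own power figure.** By two proportions with pooled null variance, 90 versus 270:

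- pooled p = (40 + 54)/360 = 0.261
- null SE = sqrt(0.261 × 0.739 × (1/90 + 1/270)) = 0.0535
- alternative SE = sqrt(0.444 × 0.556/90 + 0.20 × 0.80/270) = 0.0578
- power = Φ((0.244 − 1.96 × 0.0535)/0.0578) = 99.2%

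The stated 80% does not reproduce; the inputs give much more. That is a separate matter and does not affect this point.

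**2. Power at each ratio.** The Schoenfeld check assumes proportional hazards: HR = ln(1 − 0.444)/ln(1 − 0.20) = 2.63, and power = Φ(sqrt(events × a(1 − a)) × ln HR − 1.96), with a the trial's share of patients.

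| Participants | Ratio | Controls | Two proportions | Schoenfeld |
|---|---|---|---|---|
| 75 | 1:3 | 225 | 98.0% | 96.0% |
| 75 | 1:5 | 375 | 98.8% | 96.4% |
| 90 | 1:3 | 270 | 99.2% | 98.2% |
| 90 | 1:5 | 450 | 99.6% | 98.4% |

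The ratio moves power by less than one percentage point.

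**3. Control count.** 75-90 × 3 = 225-270; 75-90 × 5 = 375-450. The difference is 150-180 controls, or 67%. The 1:5 figure is a maximum, because a caliper or exact matching can leave sets short.

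**4. Precision.** At 90 enrolled, the control events are 0.20 × 270 = 54 or 0.20 × 450 = 90. An unstratified approximation gives SE(log HR) = sqrt(1/40 + 1/54) = 0.209 at 1:3 and sqrt(1/40 + 1/90) = 0.190 at 1:5, about 9% narrower. At the planned effect ln(2.63) = 0.969, so z is about 4.6 and 5.1. The ratio alone would not change the conclusion.

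**5. Error if one SAP version is picked after the fact.** Take two standard normal test statistics with correlation ρ and reject if either exceeds 1.96 in absolute value. Two 1:5 control sets with no overlap, sharing the same participants, give ρ = 1/(1 + 1/5) = 0.83. Overlap raises ρ, and 0.95 is taken as a high value. The two-sided error is about 7.6% at 0.83 and 6.5% at 0.95. Both correlations are assumptions.

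**The case against.** The best defence is that the SAP is the later document (2020, against a 2018 protocol synopsis), that the protocol defers detail to it, and that the 1:3 match has simply been replaced. Within the SAP, 8(b) is written as a variation, so 8(a) reads as the base analysis. The SAP is also a one-table draft summary, and a fuller version may supply the caliper, the predictors and the label. The objective is secondary in a study designed mainly for feasibility, and no familywise error control is claimed.

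Much of this stands. It is plausible that only two analyses are live. A reader might infer three competing analyses and an error of 7-10% from reporting the best of them. The documents do not support that: it treats the superseded-looking 1:3 match as a live candidate and presumes selective reporting, of which there is no sign.

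What does not stand is the hierarchy itself. No text says that the SAP overrides the protocol or that 8(a) leads. Adding detail is not the same as changing the pool, ratio, variables and endpoint. Even on the defence's reading, 8.1.4 and 8.2 still contradict the SAP.

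**Conclusion.** The point holds as a conflict between documents plus a missing label. The two documents describe different comparisons for objective 4, and the SAP offers two versions without ranking them. The control count in 8.2 is wrong if 1:5 applies.

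A reader might also infer that the mismatch threatens power. It does not: power is about 96% or more at either ratio for 44% versus 20%, before any loss of controls to the caliper or exact matching. The gain from fixing it is a hazard ratio defined in advance and a correct control count. The 6.5-7.6% error applies only if the more favourable of 8(a) and 8(b) is selectively reported, and it rests on the assumed correlations. Because the objective is secondary, this should be corrected but does not bear on the primary SVR12 analysis.

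**What to change.** Before the registry comparison is run:

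1. Name one specification as primary in both documents, stating control source and exclusions, ratio, score or matching factors, caliper width, model stratification and endpoint. Either SAP version can serve; what matters is that one is named.
2. Reconcile the endpoint with objective 4's deceased donor transplant, in the SAP and in protocol 8.1.4 and 8.2.
3. Label the other SAP version as sensitivity, list the exact-match predictors for 8(b), and correct 9(a) to 8(a).
4. Align the synopsis, Section 4.2 (objective 4), 8.1.4 and 8.2 with the choice. If 1:5 is kept, give the controls as up to 375-450.

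The cost is a few sentences in the SAP and matching edits to the protocol. It needs no new patient data.
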